9.1.2 Cohort study

For the outcomes neonatal death, and pregnancy-related death, and postpartum bleeding, a cohort design will be employed.

Risk of neonatal (28-days postnatally) death will be compared in liveborn neonates exposed and unexposed to Spikevax in utero or during the periconceptional period. The measure of association will be the risk ratio.

Pregnancy-related deaths will be assessed by comparing deaths among pregnant women exposed and unexposed to Spikevax between 30 days before LMP and delivery date. A given pregnancy will be considered exposed from the recorded date of the first Spikevax dose receipt. The measure of association will be mortality rate ratio.

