9.2.2 Exclusion Criteria

Excluded will be pregnancies with exposure to known teratogenic medications/infections or chromosomal anomalies (for analysis of malformations) and pregnancies with unavailable information on data on pregnancy start or end. Main analyses will be restricted to women without exposure to COVID-19 vaccines other than Spikevax during pregnancy.

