9.3. Variables

9.3.1 Exposure

The exposure will be defined by a record of receipt of at least one dose of Spikevax during pregnancy.

For the purposes of timing of exposure, trimesters of pregnancy will be defined as follows:

- First trimester: from the first day of the last menstrual period (LMP) to LMP+97 days (both dates inclusive);
- Second trimester: from LMP+98 days to earliest of (LMP+202 days, pregnancy end) (both dates inclusive);
- Third trimester: from LMP+203 days (inclusive) until pregnancy end date (not included)

Pregnancies unexposed to Spikevax vaccine will be categorized as unexposed or as exposed to other COVID-19 vaccines and other non-COVID-19 vaccines (influenza, meningococcal disease, pneumococcal disease, rubella, shingles, tuberculosis), overall and trimester-wise. Pregnancies among women who received Spikevax before LMP will be enumerated and may be used as an additional comparator, group size permitting.

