9.7.2 Measures of occurrence and measures of association

Prevalence of each outcome will be computed as number of observations with a given outcome divided by the total number of study population members. For neonatal death, a 28-day mortality risk will be the measure of occurrence among live-born infants. Prevalence/risks will be compared according to predefined exposure categories and using, whenever necessary,

plausible exposure risk windows. For example, for assessing the outcome of congenital malformations, births will be classified based on their exposure in the first trimester. For all other neonatal outcomes, exposure any time in pregnancy and per trimester may be considered.

Table 4 summarizes outcome-specific analysis populations and exposure windows.

Table 4 Summary of outcome-specific analysis populations and relevant exposure windows

Outcome	Analysis population	Relevant exposure window
Hypertensive disorders of pregnancy (preeclampsia, eclampsia, gestational hypertension)	All pregnancies	1st or 2nd trimester
Gestational diabetes	All pregnancies	1st or 2nd trimester
Bleeding during pregnancy	All pregnancies	1st or 2nd trimester
Postpartum haemorrhage	All pregnancies	Any time during pregnancy
Pregnancy-related death	All pregnancies	Any time during pregnancy
Fetal death (spontaneous abortion or stillbirth)	A combined population of stillbirths, livebirths, and pregnancies ending in a spontaneous abortion	Any time during pregnancy
Termination of pregnancy for fetal anomaly (TOPFA)	All pregnancies	Any time during pregnancy
Any elective pregnancy termination	All pregnancies	Any time during pregnancy
Ectopic pregnancy	All pregnancies	Any time during pregnancy
Fetal growth restriction/small for gestational age (SGA)	Live births	Any time during gestation
Preterm birth (<37 full gestational weeks)	Live births	Any time during gestation
Low birth weight (<2500 g)	Live births	Any time during gestation
Major congenital malformations	Live or stillbirths/TOPFA (whenever available) without evidence of teratogenic exposure or infection or chromosomal anomaly	First trimester
Microcephaly (based on head circumference)	Live births without evidence of teratogenic exposure or infection or chromosomal anomaly	Any time during gestation
Low 5-minute Apgar score	Live births	Any time during gestation
Neonatal death (death within 28 days of birth)	Live births	Any time during gestation

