9.7.3 Methods to control/assess confounding

Crude and adjusted measures of association will be computed comparing the exposed vs the unexposed (prevalence ratios, risk ratios, mortality rate ratios). Adjustment will be performed by the covariates measured, with LMP as the anchor date. Covariates will be included in the

appropriate regression model: log-binomial regression for prevalences and risks and Cox proportional-hazards regression for incidence rate ratios. Candidate covariates for inclusion in the analyses will vary by database. A propensity-score based adjustment may be considered and will be described in a separate Statistical Analysis Plan. Table 5 shows country-specific availability of the covariates.

Table 5 Proposed candidate covariates and data availability in participating databases

Variable/data type	AVAILABILITY OF DATA IN THE DATABASE (either via diagnosis code or procedure or treatment proxy)				
	DENMARK (NATIONAL REGISTRIES)	ITALY/ARS TOSCANA	NORWAY (NATIONAL REGISTRIES)	SPAIN/SIDIAP	UK/CPRD
Pregnancy feasibility counts for interim reports	Hospital-based ICD-10 codes for pregnancy related diagnoses or codes for prenatal visits from the Insurance registry for primary care prenatal visits	Hospital-based ICD-10 codes for pregnancy related diagnoses or codes for prenatal visits from the Insurance registry for primary care prenatal visits	All pregnancies in Norway that last at least 12 weeks are captured in the Medical Birth Registry of Norway (mandatory notification to the registry, 100% coverage)	Most pregnancies will be identifiable in primary care; some might be missed without linkage to hospital data	Pregnancy information will be available in the main primary care dataset following primary care and/or secondary care contact with the patient. This will be based on Read and/or SNOMED codes.
Country of residence	YES	YES	YES	YES	YES
Calendar year of delivery	YES	YES	YES	YES	YES
Pregnant woman's age	YES	YES	YES	YES	YES
Marital or cohabiting status	YES	To be verified	YES	To be verified	YES
Smoking	YES	To be verified	YES	YES	YES
Alcohol use (also ICD codes)	YES, IF BASED ON ICD CODES	YES	YES, IF BASED ON ICD CODES	To be verified	YES

Confidential

Post-marketing safety study for COVID-19 mRNA-1273 vaccine

Protocol mRNA-1273-P905, Date: 27 September 2021, Version 1.2

Marital status or other available socioeconomic measures	YES	YES	YES	YES Other available socioeconomic measures	YES
Gravidity	YES	YES	YES	YES	YES
Parity	YES	YES	YES	YES	YES

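### Any-time exposure windows for outcomes that end or shorten pregnancy tie the chance of being exposed to pregnancy length, which biases the prevalence ratios downward

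*Protocol*

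**What the plan says.** Section 9.3.1 of the protocol gives a single exposure rule: "The exposure will be defined by a record of receipt of at least one dose of Spikevax during pregnancy". The last window runs to the end of pregnancy: "Third trimester: from LMP+203 days (inclusive) until pregnancy end date (not included").

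Table 4 in section 9.7.2 then assigns a window to each outcome. For fetal death the population is "A combined population of stillbirths, livebirths, and pregnancies ending in a spontaneous abortion" and the window is "Any time during pregnancy". Termination for fetal anomaly, any elective termination and ectopic pregnancy have the same window, with all pregnancies as the population. Preterm birth is analysed in live births with exposure at any point of gestation. Trimester-specific exposure is optional: "For all other neonatal outcomes, exposure any time in pregnancy and per trimester may be considered".

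Section 9.1.1 makes the prevalence ratio the measure of association for these outcomes. Section 9.7.3 names the models: "log-binomial regression for prevalences and risks and Cox proportional-hazards regression for incidence rate ratios". Exposure that starts on the dose date appears only in section 9.1.2, for pregnancy-related death: "A given pregnancy will be considered exposed from the recorded date of the first Spikevax dose receipt". Section 9.2.2 adds a restriction: "Main analyses will be restricted to women without exposure to COVID-19 vaccines other than Spikevax during pregnancy".

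**The concern.** In a log-binomial model of ever against never exposed there is no time axis. A pregnancy lost at week 10 had ten weeks in which a dose could be recorded, while a term pregnancy had about forty. A dose at week 38 makes a term birth exposed, although preterm birth was no longer possible by then. A dose at week 30 adds an exposed non-case to the miscarriage and ectopic comparisons.

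The outcome therefore sets the opportunity for exposure. The probability of a dose before pregnancy end cannot fall as pregnancy length rises, so with no effect the expected ratio is at or below 1. Covariates anchored at LMP, or a propensity score built from them, cannot repair this because the imbalance arises after LMP.

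These are primary safety outcomes and the error runs towards false reassurance.

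**Working it through.** **1. The plan's own precision figure.** For spontaneous abortion, Table 3 uses prevalence 0.2 in both groups, 16,667 exposed, allocation 1:5 and a true ratio of 1.

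- SE of the log ratio = √[0.8/(16,667 × 0.2) + 0.8/(83,335 × 0.2)] = 0.01697.
- Upper limit = exp[(1.96 + 0.842) × 0.01697] = 1.049 at 80% probability, and exp[(1.96 + 1.282) × 0.01697] = 1.057 at 90%.
- Table 3 prints 1.05 and 1.06, so it reproduces. Its spontaneous-abortion rows run from 1.05 to 1.24. The 95% interval around a null ratio at this size is exp(±1.96 × 0.01697) = 0.97 to 1.03.

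**2. Expected ever/never ratio with no vaccine effect.**

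From the protocol: abortion prevalence p = 0.2, and exposed shares 1/6, 1/11 and 1/21 (allocation 1:5, 1:10, 1:20). Assumed, because the protocol does not give them: the day of loss or preterm delivery, all other pregnancies ending at day 280, preterm prevalence 6%, and a constant dose hazard h from a start day s.

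- P(exposed | length T) = 1 − exp[−h(T − s)] for T > s, otherwise 0. Call this e₁ for cases and e₀ for non-cases.
- h is chosen so that p·e₁ + (1 − p)·e₀ equals the exposed share S.
- Ratio = (p·e₁/S) ÷ [p(1 − e₁)/(1 − S)].

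Worked case: loss at day 70, s = 0, S = 1/6. Then h = 0.000775 per day, e₁ = 0.0528 and e₀ = 0.1951, and 0.2 × 0.0528 + 0.8 × 0.1951 = 0.1667 as required. Risk in exposed = 0.01056/0.1667 = 0.063. Risk in unexposed = 0.2 × 0.9472/0.8333 = 0.227. Ratio = 0.28.

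| Outcome | Case ends at | Doses from | Null ratio over the three shares |
|---|---|---|---|
| Spontaneous abortion | day 42 | LMP | 0.17–0.18 |
| | day 70 | LMP | 0.28–0.29 |
| | day 112 | LMP | 0.44–0.45 |
| | day 112 | LMP+98 | 0.09 |
| | before day 98 | LMP+98 | 0 |
| Preterm birth (6%) | day 196 | LMP | 0.69–0.71 |
| | day 252 | LMP | 0.90 |
| | day 252 | LMP+203 | 0.63–0.65 |

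**3. Does time-dependent exposure remove it?** One million pregnancies were simulated with no effect and one sixth exposed. Losses were uniform over days 35–140 and preterm births (6%) uniform over days 210–259. The same data were analysed as ever/never, and with exposure switching on at the dose within each gestational day (Mantel-Haenszel rate ratio).

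| Outcome | Doses from | Ever/never | Time-dependent |
|---|---|---|---|
| Spontaneous abortion | LMP | 0.34 | 0.99 |
| | LMP+98 | 0.06 | 1.02 |
| Preterm birth | LMP | 0.84 | 1.01 |
| | LMP+98 | 0.73 | 0.99 |
| | LMP+203 | 0.40 | 1.01 |

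**4. The other-brand exclusion.** Take weekly hazards of 0.003 (Spikevax) and 0.012 (other brands), loss at week 9, term at week 40 and p = 0.2. If the two dose times are independent, the null ratio is 0.26 without the exclusion and 0.28 with it. If the brands compete, so that only the first one is received, it is 0.31 without and 0.23 with. The direction depends on an assumption that the protocol does not settle.

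**The case against.** *The windows belong to the SAP.* Section 9.3.2.1 does defer etiologically relevant windows and population restrictions to it. But Table 4 already states the windows, and sections 9.1.1 and 9.7.3 fix the measure and the model. A SAP that follows them inherits the bias; one that corrects it departs from the protocol.

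*The protocol acknowledges the problem.* Section 9.9 says that short pregnancies may be over-represented because pregnancies are identified when they end. That is a different issue from unequal time in which to be vaccinated. The checklist in Annex 2 ticks time-related bias with a reference to 9.7.4, which is the subgroup section and does not deal with it.

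*Other comparators or trimester analyses would balance it.* A comparator given another vaccine during pregnancy might do so in part, but section 9.7.5 only allows that it may be explored. First-trimester exposure keeps the problem for early losses, and third-trimester exposure keeps it for preterm birth.

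*The size is not known.* This stands. Norway's birth registry captures pregnancies of at least 12 weeks (Table 5), and unrecorded early losses are undetectable (section 9.9). Later losses bring the ratio nearer to 1. Late dosing pulls the other way: section 7 reports a Danish recommendation for the second or third trimester. If nearly all doses preceded the earliest outcomes, the bias would be close to nil.

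A reader might also infer that excluding other-brand recipients makes the bias worse. Step 4 shows that this is not established. Nor does the first-trimester window in section 9.3.1 need a cut-off at pregnancy end, because a dose must already fall within pregnancy to count.

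**Conclusion.** The concern holds. The any-dose definition, the Table 4 windows and a model without a time axis together place the null ratio at or below 1 for fetal death, both termination outcomes, ectopic pregnancy and preterm birth. Nothing in sections 9.3.2.1, 9.7.5 or 9.9 corrects it.

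The direction follows from the definitions. The size rests on assumed dose and outcome timing and should be read as a wide range: about 0.17 to 0.45 for spontaneous abortion with doses spread from LMP, and about 0.09 or less if doses start at LMP+98 and losses occur by day 112. For preterm birth it is about 0.69 to 0.90 with doses from LMP, and 0.63 to 0.65 at day 252 with doses from LMP+203. No size was computed for terminations or ectopic pregnancy.

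For spontaneous abortion this far exceeds the sampling error that Table 3 plans for. Even at the mild end, a true doubling would show as roughly 2 × 0.45 = 0.90.

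Two stronger readings are not supported. Short pregnancies do not all fall into the unexposed group; they are more likely to. And a real increase would not always be hidden; that depends on its size and on when doses are given.

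**What to change.** For these five outcomes, make exposure time-dependent on the gestational-age scale: unexposed until the first Spikevax dose, exposed after it. Use Cox or pooled logistic regression, with delayed entry specified per database according to when pregnancies become detectable. Alternatively, match each exposed pregnancy to an unexposed one still ongoing at the same gestational day.

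Count only doses given while the outcome can still occur; for preterm birth that means before 37 weeks. Censor at a dose of another brand instead of excluding a pregnancy because of later receipt.

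Amend Table 4, the model statement in section 9.7.3, and the design statements in the abstract and sections 8.2 and 9.1.1, which assign these outcomes to the prevalence design.

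Cost: a change of declared design plus programming. No new data are needed, since LMP, end and dose dates are already required, and section 9.1.2 already starts exposure at the dose date for pregnancy-related death. These outcomes would be reported as hazard ratios or matched risk ratios. Estimated LMP dates and incomplete capture of early losses will limit precision in early gestation.

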9.3.2 Outcome

9.3.2.1 Primary outcomes

The following outcomes will be assessed, noting that outcome-specific analytic considerations such as the etiologically relevant exposure window and specific additional population restrictions (e.g., exclusion of women with teratogenic medication exposure or teratogenic infections for assessment of major congenital malformations) will be defined in the SAP.

- Pregnancy complications are:
 - Hypertensive disorders of pregnancy (preeclampsia, eclampsia, gestational hypertension)
 - Gestational diabetes
 - Bleeding during pregnancy
 - Postpartum haemorrhage
 - Pregnancy-related death

- Adverse pregnancy outcomes are:
 - Fetal death (spontaneous abortion or stillbirth)
 - Termination of pregnancy for fetal anomaly (TOPFA)
 - Any elective pregnancy termination
 - Ectopic pregnancy

- Adverse neonatal outcomes are:
 - Fetal growth restriction/small for gestational age (SGA), using sex- and gestational-age specific cutoffs¹³
 - Preterm birth (<37 full gestational weeks)
 - Low birth weight (<2500 g)
 - Major congenital malformations¹⁴
 - Microcephaly (based on head circumference)
 - Low 5-minute Apgar score
 - Neonatal death (death within 28 days of birth)

Where a signal is detected for the outcome of major congenital malformation as a composite, organ system-specific analyses will be conducted. Organ-specific major congenital malformations, according to the EUROCAT¹⁴ classification are:

- Nervous system
- Eye
- Ear, face and neck
- Congenital heart defects
- Respiratory

- Oro-facial clefts
- Digestive system
- Abdominal wall defects
- Urinary
- Genital
- Limb
- Other

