9.7.4 Subgroup analyses

All relevant analyses will be stratified by country, maternal age, sex, calendar time, trimester and seasonality if applicable and in subgroups specified in Section 9.3.4 where sample size permits.

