9.7.5 Sensitivity analyses

The following sensitivity analyses of the primary outcomes will be conducted:

- Using the date of pregnancy start as (LMP – 30 days) as an alternative definition to correct for imprecisions in LMP determination
- Alternative comparators may be explored, including contemporaneous other vaccinations (eg. influenza) or pregnancies vaccinated before LMP
- Repeating the analysis to examine the association between receipt of Spikevax in the 2nd or 3rd (but not 1st) trimester and a given major congenital malformation outcome. This is a negative control exposure analysis because exposure beyond 1st trimester cannot plausibly cause malformations, and any observed association will be due to bias.¹⁸
- Different definitions of SGA will be examined:
 - o birth weight below 2 standard deviations from sex- and gestational-week specific mean birth weight (a more specific definition, with expected prevalence of SGA of about 1%);
 - o birth weight below 10th percentile of sex- and gestational-week specific mean birth weight (more sensitive definition, with expected prevalence of SGA of about 10%)

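### Ectopic pregnancy: the any-time exposure window in Table 4, combined with a plain prevalence ratio, biases the ratio far below 1, so a null or harmful effect would look protective

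*Protocol*

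**What the plan says.** Section 9.3.2.1 lists ectopic pregnancy among the primary outcomes, and section 9.1.1 places it in the prevalence design, with the prevalence ratio as the measure of association. The Table 4 row reads "Ectopic pregnancy All pregnancies Any time during pregnancy". The general definition in section 9.3.1 is equally wide: "The exposure will be defined by a record of receipt of at least one dose of Spikevax during pregnancy".

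Elsewhere the protocol narrows windows to doses that could act. Section 9.7.2 refers, where needed, to "plausible exposure risk windows. For example, for assessing the outcome of congenital malformations", and limits malformations to first-trimester doses. Section 9.7.5 gives the reason: "exposure beyond 1st trimester cannot plausibly cause malformations, and any observed association will be due to bias". In Table 4, hypertensive disorders, gestational diabetes and bleeding during pregnancy also leave out the third trimester.

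Section 9.3.2.1 assigns to the SAP "outcome-specific analytic considerations such as the etiologically relevant exposure window". Section 9.7.4 adds: "All relevant analyses will be stratified by country, maternal age, sex, calendar time, trimester and seasonality if applicable". Section 9.3.1 ends the first trimester at LMP+97 days.

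**The concern.** Two things go wrong together.

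- **Doses that cannot act are counted.** The site of a pregnancy is settled at implantation. A dose in the second or third trimester cannot make an intrauterine pregnancy ectopic, yet the row treats it as relevant. The protocol excludes doses for malformations on this reasoning but does not apply it here.
- **The two groups have unequal time in which to be vaccinated.** An ectopic pregnancy is over within weeks, while a pregnancy ending in birth offers about 40 weeks. In a plain exposed-versus-unexposed comparison, the long pregnancies fill the exposed group and the short ones fall into the unexposed group, whatever the vaccine does.

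The second effect dominates. At stake is a primary safety outcome for which the analysis would report apparent protection under no effect, and under a doubling of risk as well.

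**Working it through.** **The plan's own figure.** No figure is given for ectopic pregnancy. The nearest is Table 3 (section 9.5), needed here only to cost the fix. With n1 exposed, n0 comparators and prevalence p:

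upper limit = exp{(1.96 + z) × √[(1−p)/(n1·p) + (1−p)/(n0·p)]}, with z = 0.8416 for 80% and 1.2816 for 90%.

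First row: n1 = 16,667, n0 = 83,333, p = 0.01. The square root is √(0.00594 + 0.00119) = 0.0844, giving exp(2.8016 × 0.0844) = 1.27 and, at 90%, 1.31. Both match the table.

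**Inputs for the bias.**

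- From the documents: the any-time window, the prevalence ratio, the first trimester ending at LMP+97, and exposed fractions f of 1/6, 1/11 and 1/21 (Table 3 allocation ratios 5, 10 and 20).
- Assumed: a constant daily chance of a first dose from LMP, other pregnancies lasting 280 days, ectopic pregnancies ending at LMP+42 to LMP+70, ectopic prevalence 1%, and a dose effect confined to the first 21 days.

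**Method.** Let h = −ln(1−f)/280, and let F(t) = 1 − exp(−h·t) be the probability of a first dose within t days. For f = 1/6, h = 0.000651, F(21) = 0.0136, F(42) = 0.0270 and F(280) = 0.1667.

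*True ratio 1.0, ectopic end at LMP+42:*

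- Exposed ectopic: 0.01 × 0.0270 = 0.00027.
- All exposed: 0.00027 + 0.99 × 0.1667 = 0.1653. Prevalence in exposed = 0.00163.
- Unexposed ectopic: 0.00973 of 0.8347. Prevalence in unexposed = 0.01166.
- Ratio = 0.00163/0.01166 = **0.14**.

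*True ratio 2.0, same setting:*

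- Baseline prevalence p0 = 0.01/(1 + 0.0136) = 0.00987.
- Exposed ectopic: 2 × 0.00987 × 0.0136 + 0.00987 × (0.0270 − 0.0136) = 0.00040.
- All exposed: 0.1653. Prevalence in exposed = 0.00242.
- Unexposed ectopic: 0.00960 of 0.8347. Prevalence in unexposed = 0.01150.
- Ratio = **0.21**.

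Over all three exposed fractions and ectopic ends from LMP+42 to LMP+70:

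| Window | True 1.0 appears as | True 2.0 appears as |
|---|---|---|
| Any time (Table 4) | 0.14–0.25 | 0.21–0.32 |
| First trimester (to LMP+97) | 0.42–0.72 | 0.64–0.93 |
| First 21 days | 1.0 | 2.0 |
| LMP to LMP+28 | 1.0 | 1.73 |

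The last row shows the price of a window somewhat wider than the assumed 21 days: mild dilution, with no reversal and no bias at the null.

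**Share of doses that can act.** In a 280-day pregnancy, F(21)/F(280) is about 8%. Moving implantation between 14 and 28 days gives 14/280 = 5% to 28/280 = 10%. The any-time results for a true ratio of 1.0 do not use the implantation date at all. They depend only on dose timing and on when ectopic pregnancies end.

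**Precision after narrowing** (100,000 pregnancies, 16,667 exposed, doses evenly spread over an assumed 275 days). A 22-day window keeps 16,667 × 22/275 = 1,333 exposed; a 29-day window keeps 16,667 × 29/275 = 1,758. The upper limits that can be ruled out with 80% probability are:

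| Assumed ectopic prevalence | 22 days | 29 days |
|---|---|---|
| 0.5% | 2.97 | 2.59 |
| 1% | 2.16 | 1.96 |
| 2% | 1.72 | 1.60 |

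**The case against.** **The window is left to the SAP.** Section 9.3.2.1 does defer outcome-specific windows, and Table 4 is presented as a summary. But Table 4 prints a value for this row, and a SAP that follows it would inherit the bias. This limits the point without removing it.

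**Other analyses cover it.** Trimester stratification removes doses after LMP+97, but the bias within the first trimester remains large. The sensitivity analysis starting at LMP−30 moves the beginning of the window, not its end. Counting a pregnancy as exposed only from the dose date is stated in section 9.1.2 for pregnancy-related death alone. Section 9.9 warns that short pregnancies may be over-represented but does not address their shorter time for vaccination.

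**Key dates come from outside the documents.** This stands. Neither the day of implantation nor the gestational age at which ectopic pregnancies end is given, so both are assumptions here.

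Some readings a reader might infer are not supported:

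- *That the protocol flatly contradicts itself.* Section 9.7.2 narrows windows only where necessary, so this is a choice out of line with its own reasoning, not a contradiction.
- *That the effect is simple dilution towards 1.* That requires exposure handled correctly in time, which the plan does not provide for this outcome.
- *That most doses in every group are irrelevant.* The 8% describes full-length pregnancies. If implantation falls at LMP+21 to +28 and ectopic pregnancies end at LMP+42 to +63, between 21/63 = 33% and 28/42 = 67% of doses given before the end of an ectopic pregnancy could act.
- *That LMP+21 is an established cut-off.* The documents do not give one, and sections 9.7.5 and 9.9 both treat LMP as imprecise.

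**Conclusion.** The point holds. As written, the Table 4 window for ectopic pregnancy and the planned prevalence ratio would give a ratio biased well below 1. The direction follows from the shorter time in which an ectopic pregnancy can be vaccinated, and needs no exact implantation date.

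The size depends on the stated assumptions, chiefly even dose timing and ectopic pregnancies ending at LMP+42 to LMP+70. The apparent ratios in the first table illustrate the size and do not forecast the study's result. If doses fall mainly in the second and third trimesters, as the Danish recommendation described in section 7 suggests for that country, the bias is larger.

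**What to change.** In Table 4, replace the ectopic window with an early one that closes at about implantation, for example LMP to LMP+28 days. Compare pregnancies with a dose in that window against pregnancies with none in it, whatever was given later. Restrict both groups to pregnancies still under way when the window closes. Because LMP is imprecise, add two sensitivity analyses: one closing the window at LMP+21 and one starting it at LMP−30 days. Keep the any-time result as descriptive only, and have the SAP carry the same window.

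The cost is fewer exposed pregnancies and wider intervals. In Table 3's largest scenario, a 22-day window leaves about 1,330 exposed and an 80% upper limit of about 2.2 at an assumed 1% ectopic prevalence (about 3.0 at 0.5%, 1.7 at 2%). A 29-day window does somewhat better. These limits are optimistic if doses are concentrated later in pregnancy, and Table 3 counts births whereas this row uses all pregnancies. Errors in LMP will also misplace some doses in so short a window, which is why the sensitivity analyses are needed.
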